### **User Satisfaction**

User satisfaction will be evaluated by a questionnaire (Appendix F). The physicians who conduct the procedures will be asked to answer questions related to usability and efficacy of Pure-Vu.

User satisfaction will be summarized in a table via descriptive statistics by data type. Chi-square or Fisher's exact test, as appropriate, will be performed in order to compare the user satisfaction between the two study arms.

## **12.5 Analysis Populations**

Cases withdrawn prior to the Pure-Vu procedure and those with technical failure will be excluded from the efficacy analysis. All patients who undergo bowel preparation will be included in the safety analysis.

Individual listings of withdrawal / failure including descriptive information will be provided.

In addition, in cases of incomplete procedure (i.e., the entire colon is not visualized); the overall BBPS per patient will be evaluated based on the colon segments that were visualized.

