### 3.0 Protocol Synopsis

Study Summary					
Study Purpose	To determine the optimal bowel preparation regimen for Pure-Vu System procedures in patients indicate for colonoscopy procedure.				
Objective	The primary objective of this multicenter, prospective, randomized study is to evaluate the performance of Pure-Vu System in cleansing patients' colon who are indicated for a colonoscopy procedure using one of two different reduce bowel preparation regimes.in addition, the cecum intubation rate, time to cecum, total procedure time, and adverse event will be evaluated.				
Test and Comparator Procedures	Prep A	Prep B			
5 days prior procedure day					
No seedy food					
1 day prior procedure day					
Low residue diet;					
Spilt dose of 15 oz Magnesium Citrate + 39 oz of clear liquid		Spilt dose of 10 oz Magnesium Citrate + 32oz of clear liquid			
Procedure Day					
Clear-liquid diet up to 3 hours prior to the procedure					
Fasting (no food / liquids) start 3 hours prior to procedure time					
*At least 2 liter water per day during the preparation days.					

Document title:  Optimizing the Preparation Regime Prior to Colonoscopy Procedure with Pure-Vu System	Document No.  CL00042	Version  1.0	Page 8 of 61
---	------------------------------------	---------------------------	-----------------

Protocol Number	CL00042
Protocol Title	Optimizing the Preparation Regime Prior to Colonoscopy Procedure with Pure-Vu System Rev 1.0
Study Sponsor	Motus GI Medical Technologies, [name] [contact] [contact]
Sponsor Representative	[name] Director of Clinical Affairs
Study Type	Multicenter, prospective, randomized feasibility study
Study Product	Pure-Vu System
Study Phase	Post-market
IDE Number	K173392 Class II
Study Location	United States
Study Duration	Study period will last approx. 12 months
Study Design	Patients will be randomized to receive one of two bowel preparation regimens prior to colonoscopy with Pure-Vu procedure.
Planned Follow-Up	Telephone follow-up will be conducted at 2-3 working days post-procedure to assess subject well-being and capture any adverse events.
Subject Population	Subjects indicate for colonoscopy procedure

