### 10.3 Withdrawal Criteria

Subjects may withdraw from the study at their own request or at the request of their legally acceptable representative. The investigator may withdraw a subject from the study at any time for the following reasons:

- Severe side effects clearly related to the study device.
- Presence or appearance of exclusion criteria.
- Appearance of accompanying diseases rendering further participation in the study impossible.
- A significant protocol violation, as determined either by the sponsor or the investigator
- Subject noncompliant with investigational procedures
- Subject noncompliant with visits
- At the specific reasonable request of the sponsor

The sponsor must be informed in each withdrawal case. The reason for withdrawal must be recorded in the CRF and in the patient file.

Document title:	Document No.	Version	Page 25 of 61
Optimizing the Preparation Regime Prior to Colonoscopy Procedure with Pure-Vu System	CL00042	1.0	

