#### **Recruitment visit:**

Patients who meet the eligibility criteria will be screened for study participation and will be randomly allocated to a given study arm at a baseline visit. Patients who are eligible for the study will be required to follow a specific bowel preparation instruction along with a specific prep agent, (Detailed instructions of the study Bowel preparations are provided in appendix B1 and B2) as per study arm allocation, starting 5 days prior to the colonoscopy with Pure-Vu. Subject diaries are provided to the subject at visit 1 to be and will be filled by the subjects during the preparation phase. This will include diet and bowel movement information (diary log is provided in appendix D). The subject is instructed to bring the diary with him/her to the scheduled colonoscopy.

In addition patient satisfaction questionnaire will be provide include feedback on the procedure and on specific aspects related to the preparation regime.

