#### **11.1.2 Randomization**

Randomization in blocks will be applied for each site to allocate patients to one of two different bowel preparation regimens (Prep A versus Prep B). The study will utilize randomization in blocks using the standard envelope procedure, which will be applied in order to allocate patients into two arms:

- Group 1 - Will go through the Prep A procedure
- Group 2 - Will go through the Prep B procedure

The site randomization plan will be provided to the study coordinator prior the study start. No blinding is applicable in this study.

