#### **11.1.5 Colonoscopy procedure (Visit 2)**

##### Pre-Examination Procedures

- Verify eligibility checked and informed consent was obtained after explaining all risks, benefits, and alternatives to the candidate.
- Verify that the research assistant has collected completed diaries from the subject.
- Verify all background/clinical information, demographic and medical history was documented

Note: Subjects that did not take the bowel preparation or failed to complete the bowel preparation will not undergo the procedure and will be excluded from the study.

- Verify all connections and assembles are properly attached (see Instructions for Use)
- Verify device works properly (see Instructions for Use)
- Place and prepare the subject for the procedure as per standard colonoscopy.
- Perform a digital rectal exam as per standard colonoscopy, evaluate the adequate level of the preparation and start the colonoscopy procedure with the Pure-Vu System as per standard of care.

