### **12.2 Description of statistical methods**

Basic demographic and other baseline characteristics will be collected and analyzed for all patients. Summary statistics (arithmetic mean, standard deviation, median, minimum and maximum for quantitative variables) will be presented for the total study population. Frequency tables for qualitative data will be provided.

Any deviation from specified statistical plan will be in addition to “per protocol” analysis and will be reported as such. Intent-To-Treat and Post-hoc analysis will be conducted according to the existing data gathered, if necessary.

In addition, in cases of an incomplete procedure (i.e., the entire colon is not visualized); the overall BBPS per patient will be evaluated based on the colon segments that were visualized.

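### Choosing between Prep A and Prep B rests on examined patients only: non-completers, pre-procedure withdrawals and technical failures drop out after randomisation, and intention-to-treat is optional

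*Protocol*

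**What the plan says.** The bowel preparation is the randomised intervention (Protocol 11.1.2). Under the recruitment visit in Section 11.1.1, eligible patients "will be randomly allocated to a given study arm at a baseline visit", before the preparation starts. Section 11.1.2 adds: "No blinding is applicable in this study".

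Three rules then decide who is compared:

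- Section 11.1.5: patients who did not take the prep or "failed to complete the bowel preparation will not undergo the procedure and will be excluded from the study".
- Section 12.5: "Cases withdrawn prior to the Pure-Vu procedure and those with technical failure will be excluded from the efficacy analysis".
- Section 12.2 treats a per-protocol analysis as the reference and continues: "Intent-To-Treat and Post-hoc analysis will be conducted according to the existing data gathered, if necessary".

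The investigator's grounds for withdrawal in Section 10.3 include "Subject noncompliant with investigational procedures". For safety, Section 12.5 is wider: "All patients who undergo bowel preparation will be included in the safety analysis". It also requires individual listings of withdrawals and failures.

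The synopsis gives the study purpose as "To determine the optimal bowel preparation regimen for Pure-Vu System procedures". Section 12.7 says the study should indicate whether Prep B looks better than Prep A, to inform later research.

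**The concern.** Completing the prep follows allocation and may be affected by it. An analysis restricted to patients who completed the prep and were examined therefore conditions on a post-randomisation event. For the question of which regimen is better, that weakens the protection randomisation gives. If one regimen is harder to finish, its non-completers leave the adequacy rate instead of counting against it. Some pre-procedure withdrawals are also judgements made with the arm known.

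At stake is the direction and size of the estimate that later research would use. No powered test is at risk, because Section 12.1 says the sample size has no statistical basis.

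**Working it through.** The plan states no figure to reproduce: it gives no alpha, power, effect size or non-completion rate. The non-completion rates below are assumptions for illustration.

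**1. Is there evidence that completion differs by arm?** The synopsis prescribes 15 oz magnesium citrate with 39 oz clear liquid (Prep A) and 10 oz with 32 oz (Prep B). The sums are 15 + 39 = 54 oz and 10 + 32 = 42 oz. But both arms must also drink at least 2 liters a day (synopsis, Appendix D), and Appendix D lists 3 × 20 = 60 oz of clear liquid at meals on the day before for both. The protocol does not say whether the 39 and 32 oz come on top of this. The certain difference is 5 oz of magnesium citrate; whether total fluid differs is unclear.

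**2. Formula.** Let p be the adequacy rate among examined patients, assumed equal in both arms, and nA and nB the proportions not completing. The examined-set difference is p − p = 0. Among all randomised patients, the proportion who completed, were examined and were adequately cleansed is p(1 − nA) against p(1 − nB). The difference B − A that the examined set cannot show is p(nA − nB).

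**3. Results.** Section 6.3 gives p = 99% (95% CI 94% to 100%), from a study with a different preparation.

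| nA / nB | p | Prep A | Prep B | B − A (points) |
|---|---|---|---|---|
| 5% / 5% | 0.99 | 94.05% | 94.05% | 0 |
| 10% / 5% | 0.94 | 84.60% | 89.30% | 4.70 |
| 10% / 5% | 0.99 | 89.10% | 94.05% | 4.95 |
| 10% / 5% | 1.00 | 90.00% | 95.00% | 5.00 |

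If Prep B has the 10% and Prep A the 5%, the sign reverses.

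**4. Precision.** Section 9.0 plans 15 per arm per site. With the synopsis maximum of 3 sites that is 45 per arm; the cap of 100 patients gives 50. (Section 9.0 itself says up to 10 sites, so 45 is an assumption.) For 89.10% against 94.05%, the 95% half-width is 1.96 × √(0.891 × 0.109/n + 0.9405 × 0.0595/n). This is 11.4 points at n = 45 and 10.8 at n = 50. Two-sided Fisher power at an assumed 0.05 level is 5.8% and 6.2%.

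**5. Hypothetical counts at 45 per arm.** Suppose one arm has 3 non-completers and 42/42 adequate, and the other has 43/45 adequate.

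- Examined set: 100% against 95.6%, a difference of +4.4 points for the first arm.
- All randomised: 42/45 = 93.3% against 43/45 = 95.6%, a difference of −2.2 points.

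The ranking changes, although Fisher p is about 0.49 in the first comparison and 1.0 in the second. Each patient who moves from excluded to not achieving the outcome shifts an arm by about 2 points (1/45 = 2.2; 1/50 = 2.0).

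**The case against.** The strongest reply is that the examined set matches a comparison the protocol states. Section 5.1 ends by describing a comparison of cleansing after use of the two preps in subjects undergoing colonoscopy. Section 8.1 concerns Pure-Vu performance, and the Section 12.3 endpoint is scored after Pure-Vu use, so it does not exist without a procedure. This stands: the examined set should remain. It does not settle the wider regimen question in the synopsis and Section 12.7.

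A second reply is that counting unexamined patients as failures does not estimate cleansing. In Section 6.3, adequacy rose from 25% to 99% with the device, so an unexamined patient might well have been cleansed. This also stands. The all-randomised outcome is a composite of completion and cleansing, and should be labelled as one.

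Third, much of the information is already collected or reported: intention-to-treat is foreseen, withdrawals are listed, adverse events and patient satisfaction are summarised by arm (12.4), and completion is on the case report form. But individual listings give no between-arm estimate, and an optional analysis can be decided on after the data are seen. A SAP could add analyses, but the exclusions and the condition are fixed in the protocol itself.

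A reader might go further and infer that Prep A will lose more patients, from 54 against 42 oz or from the 38% non-completion in Section 5.1. The documents do not support this. The fluid totals may not be a real contrast, the 38% concerns bowel preparation in general, and Section 7.2 calls both study preps less intensive than standard.

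**Conclusion.** The point holds for the regimen comparison and should be fixed. As written, that comparison depends on completing the prep and reaching the procedure without technical failure, and nothing commits the study to an analysis of everyone randomised.

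The size is unknown. The hidden difference is zero if non-completion is equal and examined adequacy is the same in both arms, and 4.7 to 5.0 points if non-completion is 10% against 5% with equal adequacy of 94% to 100%. Either is small beside a half-width of about 11 points. The gain is an estimate less open to selection, not a significant result.

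It would be wrong to conclude that the examined-set analysis is invalid, or that a bias in a known direction has been shown.

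**What to change.** 1. **Section 12.2:** delete the closing condition on intention-to-treat. Commit to a supportive analysis of all randomised patients by assigned arm, beside the Section 12.5 analysis. The outcome is prep completed, examined and adequately cleansed, described as a composite. Count prep non-completion and pre-procedure withdrawal as not achieving it. Give an explicit rule for technical failures, for example counting them the same way. Add a sensitivity analysis that leaves out withdrawals and technical failures unrelated to the prep.
2. **Section 12.5:** report prep completion by arm with a 95% confidence interval, from the completion item in Appendix F. Tabulate all exclusions by arm and reason.
3. **Sections 11.1.3 and 11.1.5:** Section 11.1.3 limits follow-up to subjects who receive study-assigned procedures, and Section 11.1.5 excludes non-completers from the study. Reconcile both with the Section 12.5 safety set, so that these patients stay in the all-randomised, completion and safety reporting.

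The cost is wording. Arm and completion are already on the case report form, and Section 10.3 already requires the withdrawal reason. Who undergoes the procedure does not change. The downside is a lower composite rate beside the examined-set rate, with some unrelated withdrawals counted as failures; the sensitivity analysis shows how much they matter.

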## **12.6 Interim Analyses**

No interim analysis is planned in this study.

Document title:	Document No.	Version	Page 32 of 61
Optimizing the Preparation Regime Prior to Colonoscopy Procedure with Pure-Vu System	CL00042	1.0	

## 12.7 Potential Limitations

Several potential limitations of the study are acknowledged:

- The sample size is not statistically powered for this feasibility study. While this may limit the study interpretation, the study objective is to evaluate whether Prep B will tend to have better outcomes compared to Prep A in order to inform future clinical research studies.
- Because this study uses a standard-risk cohort, the result may not be generalizable to high-risk cohorts.

## 13.0 Adverse Events (AEs) and Complications

AE and AE subcategories are defined per ISO14155:2011, as described below.

### 13.1 Adverse Event (AE)

An AE is any untoward medical occurrence, unintended disease or injury, or untoward clinical signs (including abnormal laboratory findings) in subjects, whether or not related to the investigational medical device.

This definition includes events related to the investigational medical device or the comparator and the procedures involved.

AEs will be collected starting from the time subject is enrolled until the follow-up period is completed.

### 13.2 Serious Adverse Event (SAE)

A Serious AE (SAE) is an AE that has

- a) Led to death,
- b) Led to serious deterioration in the health of the subject, that either resulted in
  - 1) A life-threatening illness or injury, or
  - 2) A permanent impairment of a body structure or a body function, or

Document title:	Document No.	Version	Page 33 of 61
Optimizing the Preparation Regime Prior to Colonoscopy Procedure with Pure-Vu System	CL00042	1.0	

- 3) In-patient or prolonged hospitalization, or
- 4) Medical or surgical intervention to prevent life-threatening illness or injury or permanent impairment to a body structure or a body function,
- c) Led to fetal distress, fetal death or a congenital abnormality or birth defect

NOTE: Planned hospitalization for a pre-existing condition, or a procedure required by the clinical investigational plan, without serious deterioration in health, is not considered an SAE.

Some important medical events, although they may not result in death, be life-threatening, or require hospitalization may still be considered SAEs when, based upon appropriate medical judgment, they are felt to jeopardize the subject and may require medical or surgical intervention to prevent one of the outcomes listed above.

Life threatening means that the subject was, in the view of the investigator, at immediate risk of death from the reaction as it occurred. This does not include an AE that, if more severe, might have caused death.

Disability means a substantial disruption of a person's ability to conduct normal life's functions.

### **13.3 Adverse Device Effect (ADE)**

An Adverse Device Effect (ADE) is an AE related to the use of an investigational medical device.

This definition includes AEs resulting from insufficient or inadequate instructions for use, deployment, implantation, installation, or operation, or any malfunction of the investigational medical device.

This definition includes any event resulting from use error or from intentional misuse of the investigational medical device.

### **13.4 Serious Adverse Device Effect (SADE)**

A Serious Adverse Device Effect is an adverse device effect that has resulted in any of the consequences characteristic of an SAE.

Document title:	Document No.	Version	Page 34 of 61
Optimizing the Preparation Regime Prior to Colonoscopy Procedure with Pure-Vu System	CL00042	1.0	

### 13.5 Unanticipated Serious Adverse Device Effect (USADE)

An Unanticipated Serious Adverse Device Effect is a serious adverse device effect which by its nature, incidence, severity, or outcome has not been identified in the current version of the risk analysis report.

### 13.6 Adverse Event Severity Classification

Severity will be defined according to the following criteria:

Mild	Awareness of event, but easily tolerated
Moderate	Discomfort enough to cause some interference with activities of daily living (ADL)
Severe	Incapacitating, with an inability to perform ADL

An AE can be classified as severe and not deemed a SAE. Similarly, a SAE is not automatically severe in nature.

### 13.7 Adverse Event Relationship Classification

Relationship to study product administration will be determined as follows:

- *No Relationship*: No relationship between the AE and the administration of study treatment and a known relationship to other etiologies such as concomitant medications, procedure, or subject's clinical state.
- *Possible Relationship*: An AE that follows a reasonable temporal sequence from administration of the study treatment and follows a known response pattern to the study treatment but could have been produced by the participant's clinical state or by other therapies.
- *Probable Relationship*: An AE that follows a reasonable temporal sequence from administration of the study treatment; follows a known response pattern to the study treatment; and cannot be reasonably explained by the known characteristics of the participant's clinical state or by other therapies.
- *Definite Relationship*: An AE that follows a plausible temporal sequence from administration of the study treatment and follows a known response pattern to the study treatment. The reaction cannot be reasonably explained by the known characteristics of the subject's clinical state or other modes of therapy administered to the subject.

Document title:	Document No.	Version	Page 35 of 61
Optimizing the Preparation Regime Prior to Colonoscopy Procedure with Pure-Vu System	CL00042	1.0	

- *Unknown/Impossible to Determine:* Given the information available, sequence and timing of events, it is unknown or impossible to determine the relationship of the AE with the study treatment.

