### 13.10 Adverse Event Recording and Reporting

Assessment of the occurrence of an AE will be based on changes in the subject's signs and symptoms. AEs will be monitored until a subject completes the study unless the Investigator determines the event is related to the investigational device, in which case they will be monitored until resolution if possible. Medical care will be provided, as defined in the informed consent, for any AE related to study participation. AEs will be collected on an AE CRF and applicable source documentation.

The following should not be considered an AE:

Document title:	Document No.	Version	Page 36 of 61
Optimizing the Preparation Regime Prior to Colonoscopy Procedure with Pure-Vu System	CL00042	1.0	

- A condition requiring a preplanned procedure unless the condition worsened since screening
- A preexisting condition found as a result of screening, unless the condition has worsened since enrollment.

All AEs observed during the course of this study, regardless of severity or relationship to the investigational device will be recorded on the appropriate CRF.

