### **13.11 Reporting Responsibilities**

An investigator shall submit to the sponsor and to the reviewing IRB a report of any unanticipated SAEs, ADEs, SADEs, USADEs, and device deficiencies that could have led to a serious adverse device effect occurring during an investigation within 24 hours of learning of the event, but in no event later than 10 working days after the investigator first learns of the effect.

A sponsor who conducts an evaluation of an unanticipated adverse device effect under 812.46(b) shall report the results of such evaluation to FDA and to all reviewing IRB's and participating investigators within 10 working days after the sponsor first receives notice of the effect.

Thereafter the sponsor shall submit such additional reports concerning the effect as FDA requests (21 CFR Part 812.150).

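### Section 13.7 gives no positive relatedness grade to a device effect without a known response pattern, which conflicts with the nature limb of 13.5 and with the AE form

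*Protocol*

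**What the plan says.** Section 13.7 is written as the operative rule: "Relationship to study product administration will be determined as follows". It has five grades.

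- Possible is "An AE that follows a reasonable temporal sequence from administration of the study treatment and follows a known response pattern to the study treatment", where another cause could also have produced the event.
- Probable again needs reasonable timing, and the event "follows a known response pattern to the study treatment; and cannot be reasonably explained by the known characteristics of the participant's clinical state"; treatments besides the study one must likewise be ruled out as the explanation.
- Definite is "An AE that follows a plausible temporal sequence from administration of the study treatment and follows a known response pattern to the study treatment", again with no other reasonable explanation.
- No Relationship requires a known link to some other cause.
- Unknown/Impossible to Determine is for events whose relationship cannot be settled on the information available.

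The definitions upstream form a chain. Section 13.3: "An Adverse Device Effect (ADE) is an AE related to the use of an investigational medical device". Section 13.4 makes a SADE an adverse device effect with serious consequences. Section 13.5 makes a USADE a SADE which "by its nature, incidence, severity, or outcome has not been identified in the current version of the risk analysis report".

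Three places act on relatedness. Section 12.4 names the device-related AE rate as a safety outcome beside the overall rate. Section 13.10 follows AEs only until the subject completes the study unless the investigator judges the event device-related, "in which case they will be monitored until resolution if possible". Section 13.11 says: "An investigator shall submit to the sponsor and to the reviewing IRB a report of any unanticipated SAEs, ADEs, SADEs, USADEs, and device deficiencies". Only deficiencies with the potential to cause a SADE are meant.

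The adverse event form in Appendix F records relation to the study on a different scale (Unrelated, Unlikely, Possibly, Related). It gives no definitions and has a separate yes/no item for whether the event was anticipated.

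**The concern.** A relatedness scale should let an investigator say that an event was probably caused by the device even if nobody has seen that effect before. Section 13.7 does not allow this, because it joins the known-pattern condition to timing by *and* in every positive grade. Section 13.5, by contrast, exists partly to catch effects whose nature was not foreseen, and such an effect must first be device-related to enter the 13.3 to 13.5 chain.

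What is at stake is classification in the safety analysis and the actions that follow from it. Participation lasts about 8 days (Section 10.0), so whether an AE is followed to resolution or only to study completion is a real difference. The device-related rate in 12.4 could also be understated for the kind of event that a feasibility study is well placed to notice.

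**Working it through.** No figure in the protocol bears on this, so the check is a reading of the text. Take a test event: suggestive timing after the procedure, no other explanation, and no known response pattern.

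| Grade in 13.7 | Timing | Known pattern | Other cause | Does the test event fit? |
|---|---|---|---|---|
| No Relationship | none stated | none stated | a known other cause is required | No |
| Possible | reasonable | required | another cause could explain it | No |
| Probable | reasonable | required | no other reasonable explanation | No |
| Definite | plausible | required | no other reasonable explanation | No |
| Unknown/Impossible to Determine | none | none | none | Yes, the only one left |

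The condition is present in 3 of 3 positive grades. If the test event is changed so that another cause could also explain it, it still fails Possible on the pattern condition.

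Next, the four limbs of 13.5:

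- Incidence, severity and outcome: an event of known pattern that is more frequent, more severe or worse in outcome than the risk analysis report lists can be graded related and can be a USADE. These three limbs are untouched.
- Nature, known pattern but absent from the report: still reachable, because 13.7 does not tie a known pattern to that report.
- Nature, no known pattern: no positive grade is available. This is the conflict.

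So 1 of 4 limbs is affected, and that one only in part.

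Then the consequences if an event graded Unknown is handled as not device-related:

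| Rule | New non-serious effect | New serious effect |
|---|---|---|
| Recording (13.10) | recorded | recorded |
| Investigator report (13.11) | could be missed, since its main route is as an ADE | still reportable as an unanticipated SAE, which has no relatedness condition |
| Follow-up to resolution (13.10) | could be missed | could be missed |
| Device-related AE rate (12.4) | could be missed; counted in the overall rate | could be missed; counted in the overall rate |

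Whether the word *unanticipated* in 13.11 governs the whole list or only its first item makes no difference here: a new non-serious effect that is accepted as an ADE is on the list either way.

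Last, the form. Appendix F has four levels and 13.7 has five. Unlikely has no counterpart in 13.7. Probable, Definite and Unknown have no counterpart on the form. The form attaches no pattern condition, so the test event can be entered there as Related and not anticipated, while 13.7 puts it in Unknown.

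A side observation: Probable and Definite rest on the same three conditions and differ only in *reasonable* against *plausible* timing. No rule in the protocol treats the two grades differently, so this changes no action.

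**The case against.** A reader might infer that 13.7 defeats the unanticipated-effect category altogether. The documents do not support that. Three limbs of 13.5 survive intact, and the fourth survives for any known pattern that the risk analysis report omits.

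The link from grade to consequence is also inferred. Sections 13.3 to 13.5 and 13.10 do not cite the 13.7 grades. Section 13.3 covers malfunction and use error without any pattern condition, and 13.10 turns on the investigator's determination. Nowhere does the protocol say that Unknown is handled as not related. An investigator could therefore call a new effect an ADE despite 13.7. This objection stands in part: the event *could* be lost, not *will* be. But 13.7 is the only place where the protocol sets out how relationship is decided, and leaving Unknown without a stated handling is itself part of the problem.

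The AE form lets a new effect be recorded as related. That is true, but its scale is undefined and does not map to 13.7, so it adds a second inconsistency and does not cure the first.

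No serious event goes unreported, because unanticipated SAEs are on the 13.11 list regardless of relatedness. That stands, and it is why the exposure lies mainly with non-serious effects.

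It is tempting to size the problem from the 97 earlier subjects. Sections 6.3 and 7.1 report no serious adverse events or major complications in them. They do not report that no new or non-serious device effects occurred, so no rate for such effects can be drawn from that figure.

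**Conclusion.** The point holds in a limited form. As written, 13.7 leaves a device effect without a known pattern no grade but Unknown. That conflicts with the nature limb of 13.5 and with an AE form that allows a related, unanticipated event. The likely loss is a new non-serious effect missing from the device-related rate, from ADE reporting and from follow-up to resolution. For a serious one, the investigator's report is preserved, but the device-related count and the follow-up rule remain uncertain.

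This rests on two assumptions: that investigators apply 13.7 literally, and that Unknown is then taken as not related. The protocol says neither outright. How many events are affected cannot be estimated from the documents. The cleansing endpoint and its analysis are not touched.

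**What to change.** 1. In 13.7, remove the known-pattern condition from Possible. For the higher grades make it one of two routes, for example: *follows a known response pattern or is otherwise plausibly caused by the device*. Keeping it as a requirement for Definite would still bar a new effect with an evident device cause from the top grade. If Probable and Definite are both kept, say what separates them.
2. Use one relatedness scale, with the same definitions, in 13.7 and on the AE form in Appendix F. Keep the form's separate item on whether the event was anticipated.
3. State which grades count as related for 12.4, 13.10 and 13.11.
4. Report Unknown events separately, with a sensitivity count of the device-related rate that treats them as device-related. Folding them all into the main rate is debatable, because it mixes undetermined events into a device-safety outcome.

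The cost is a few words in 13.7, a short statement on which grades count as related, and a small edit to the form. A few more events may be classed as device-related, which is the cautious direction for a safety summary.
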